This Great Plains IDeA-CTR pilot project will utilize a prospective, within-participant design with multiple assessments across a 10-week intervention period and 1-month follow-up. Repeated measures optimize statistical power with smaller sample sizes and examination of within-person change over time. A 10-week intervention period was selected for this pilot project because this duration was consistent with the recommended amount of time it takes for habit formation to occur.¹ The 1-month follow-up period was chosen because of project resources and to maintain adherence to our 1-year project timeline. Our study will recruit 20 participants based on Aim 3, which provides 80% power in detecting a large standardized effect size of 0.72 in terms of change in the outcome (physical activity) after 1-month follow-up, with an alpha level of 0.05 using a two-sided Wilcoxon Sign-Ranked test, assuming that the actual data distribution is normal and a drop-out rate of 10%.² It should be noted that this is a pilot study with a smaller sample size. If the study yields smaller effect sizes when assessing the intervention effects, the study still provides useful information on feasibility, the trend of the intervention's effect, and accurate effect sizes for estimation that can be generalized to guide future large trials. Adults aged at least 65 years that can use the internet daily, have a body mass index $\geq 30 \text{ kg/m}^2$, and are apparently healthy (i.e., medically able to participate in physical activity as determined by the PAR-Q+) will be eligible for study. We will utilize the North Dakota State University Research Participation Listserv for study recruitment. Word-of-mouth and flyers will also be used for recruitment purposes. Aim 1: Collaborate with stakeholders in all-phases of the internet-based wellness intervention to gain knowledge on the perspectives of the older adult population. Conducting community-based participatory research has demonstrated effectiveness in intervention studies and its use in research should be promoted, but few intervention studies in aging research exist where older adults have a research role.³ An important component of community-based participatory research is to have stakeholders contribute to all phases of a study.⁴ Specifically, we will recruit stakeholders to engage in the formative stages of the research, study execution, data interpretation, dissemination, and translation of results to practice.⁴ The stakeholders will also provide our research with an additional perspective from the older adult population, thereby strengthening the impact of the investigation for older adults.^{5,6} We intend for this pilot project to serve as a catalyst for future research projects that expand on the use of community-based participatory research such as developing a sustainable older adult community nucleus, allowing stakeholders to have equitable decision making of future research funding, and providing services to the older adult population that are outside of research.⁴ Two stakeholders with wellness experience will be recruited from the local area through word-of-mouth and posting flyers at locations where older adults are known to gather. In order to better ensure representativeness, one stakeholder will be aged 65-69 years and the other will be aged at least 70 years. The Principal Investigator will select stakeholders for this project and they will be excluded as participants in the intervention. Based on our extant of the literature, a lack of professional guidance, inadequate distribution of appropriate educational materials, restrictions in transportation, and low motivation are barriers for older adults to engage in healthy behaviors.⁷⁻⁹ Using behavior change theoretical framework in wellness interventions has been identified as a research requirement to advance the field.¹⁰ Including motivation to engage in healthy behaviors for this project will come from two psychological theories that are often

applied to wellness motivation studies: self-determination theory and social cognitive theory.¹¹⁻¹⁴ Participation in physical activity, diet modification, and restorative sleep were targeted because they are each considered important for the health of older adults and can be impacted by motivation.^{15, 16} Didactic information (e.g., videos and readings) for the health benefits of physical activity, a healthy diet, and restorative sleep will be delivered to participants, including how each of these factors effect health and longevity. With the help of the investigators and stakeholders, participants will design their own goal-oriented program. Progression towards longer-term goals will include a stepwise process of achieving short-term goals. Modifications toward these goals can be made based on progress and discussions with each participant. Intervention usability guidelines and resources from the United States Department of Health and Human Services will be used.¹⁷ During the kick-off meeting, the investigators will introduce the initial conceptual model to the stakeholders. Discussions between the investigators and stakeholders will help to refine the strategies that will be used to enhance each construct relative to lifestyle behaviors. Investigators and stakeholders will develop a project plan and timeline, delegate roles and responsibilities, and refine the conceptual model. The contents of the internet-based wellness intervention will be uploaded on Google Classroom, a free online learning platform that can be used for administering internet-based health interventions.¹⁸ There is always a risk that our intervention will not reflect the needs and priorities of the users; therefore, prior to launching the intervention, 3-5 individuals (non-participants) will pilot the contents in Google Classroom and measurement tools to provide feedback, thereby bolstering the reliability and quality of the platform, contents and measures. During the study period, the investigators will work with stakeholders in administering the intervention. The stakeholders will act as role models for participants by sharing experiences, initiating communications and providing information. Combining the use of a role model with other motivation factors has been recognized as a facilitator for practicing healthy behaviors in intervention studies with older adults.¹⁹ Aim 2: Assess the feasibility of an internet-based wellness intervention for obese older adults. According to Bowen et al.'s²⁰ phases of intervention development, this stage of development for the intervention is key in assessing the "can it work?" components such as: acceptability, demands and implementation. These feasibility components are heavily focused on the actual use of the internet for a wellness intervention and any barriers or facilitators that participants may experience when using it. To evaluate potential efficacy, components that contribute to healthy behaviors such as acceptability, demand, and implementation will be evaluated. Specific items to be evaluated within these components include satisfaction with the platform, intent to continue, interest, recommendations to peers, usability, improved knowledge, and general recommendations for improvement. Each of the feasibility components will be evaluated with a 5-point Likert scale developed by the investigators and stakeholders, and may include open-ended items for more detailed feedback. Feasibility questionnaires will be completed online by participants at the mid-point and end of the intervention period. Participants will also be asked about their readiness to change wellness behaviors at the beginning, mid-point, and end of the intervention period by selecting their stage of change: pre-contemplation, contemplation, preparation, action, maintenance and termination.²¹ Adherence and compliance will be quantified as the proportion of participants who fully completed the intervention. Results from the feasibility examination will be presented as mean and standard deviation or frequency

and percentage where appropriate. During weekly meetings, the investigators and stakeholders will assess if they are able to effectively communicate with participants using the internet, time commitment for learning, and overall feasibility of the intervention. Guidelines from the United States Department of Health and Human Services for program evaluation will help to guide how we determine feasibility.²² Aim 3: Determine if completing an internet-based wellness intervention improves healthy behaviors among obese older adults. Participants will be asked to visit Exercise Science Labs at North Dakota State University at the beginning and end of the intervention, and at 1-month follow-up. After providing written informed consent, each participant will complete a descriptive questionnaire at the beginning of the intervention period, and a health-related questionnaire at the beginning and end of the intervention, and at follow-up that includes self-rated health, current smoking status, smoking history, alcohol use, morbid conditions, functional disability, and depression status. Standing height and waist circumference will be collected with a tape measure. Body weight and composition will be measured with the InBody 570 (InBody; Cerritos, CA). Previous research has demonstrated that the InBody 570 has strong reliability and validity for measuring body composition that is comparable to dual x-ray absorptiometry.^{23,24} Anthropometric and body composition assessments will be collected from participants at the beginning and end of the intervention, and at follow-up. 6 Objectively Measured Physical Activity and Sleep Physical activity will be collected with an ActiGraph GT9X-BT accelerometer (ActiGraph; Pensacola, FL). The ActiGraph accelerometer has strong reliability and validity for capturing free-living physical activity.²⁵ Accelerometers will be given to participants during lab visits and sent back in a pre-paid mail envelope after wearing the accelerometer for all hours of the day on their waist for 7 consecutive days. Data will be considered valid if participants wore the accelerometer for at least 10 hours/day during waking hours, for at least four days including one weekend day.²⁶ The Choi et al.²⁷ non-wear algorithm will be used for determining wear time compliance. Accelerometer specific cut-points will examine time spent sedentary and in each intensity of physical activity.^{28,29} As part of the physical activity measurements, the ActiGraph accelerometer will also measure total sleeping time. ActiGraph accelerometers have strong reliability and validity for assessing sleep.^{30,31} Participants will be asked to wear the accelerometer during sleep and record periods of sleep in a log.³² The Cole-Kripke algorithm embedded in Actilife 6 software will be used to score the sleep actigraphy.³³ Physical Activity Recall Use of time will be quantified using the Multimedia Activity Recall for Children and Adults, a computerized 24- hour recall. Each participant will recall their daily activities using a segmented day format with a resolution of 5 minutes or more. Participants choose from 500 different activities organized under a number of rubrics such as “self-care”, “occupation”, and “leisure”, with each activity linked to a compendium of energy expenditures.³⁴ The adult version shows excellent test-retest reliability and good convergent and criterion validity with accelerometers and doubly-labeled water, respectively.³⁵⁻³⁷ The Multimedia Activity Recall for Children and Adults will be administered by 30 minute computer-assisted telephone interviews, with two consecutive days being recalled each time. The same 4 days will be recalled at each time-point (intervention beginning and end, and follow-up), including at a weekday and weekend day. Dietary Recall Participants will complete the Arizona Food Frequency Questionnaire (AFFQ) to assess dietary intake at the beginning and end of the intervention, and at 1-month follow-up. The AFFQ is a modified version of the Health Habits

Questionnaire and has demonstrated strong reliability and validity for assessing dietary intake.^{38,39} The semi-quantitative, scannable, 153-item AFFQ asks respondents to report how often they consumed each particular food item during the last month. Participants will receive a report of estimated nutritional intake compared to recommendations with each AFFQ. In addition, each report will contain a personalized message from the dietitian to each participant. Intake of nutritionally dense foods (e.g., vegetables, lean proteins) and decreased intake of calorically dense foods (e.g., high sugar foods) will be compared to assess dietary change. Statistical Analysis Analyses will be conducted with SAS 9.4 software (Cary, NC). Means and standard deviations for continuous data or proportions for categorical data will be used for presenting the measures at baseline and measures at each data collection time point during the study period. Linear mixed effects models for continuous data or generalized linear mixed effects models for categorical data with fixed time effects, and random person effects will be used to evaluate changes in the outcomes. Repeated measures analysis requires consideration of the correlation between outcomes across the intervention period (covariance structures). To examine optimal covariance structures, Akaike information criterion will be used to determine the model of best fit. Potential covariates include age, sex, ethnicity, marital status, self-rated health, current smoking status, smoking history, alcohol use, morbid conditions, functional disability and depression status. Separate models will be used to assess changes in 1) physical activity, 2) diet, and 3) sleep. An alpha level of 0.05 will be used for all analyses.

2. Cohen J. Statistical power analysis for the behavioral sciences. *Ann NY Acad Sci*; 2013.

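### Adherence and compliance share one undefined yes/no completion proportion, which scores near-complete use the same as no use; no other Aim 2 tool is stated to measure amount of use

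*Combined protocol and SAP*

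**What the plan says.** The combined protocol and SAP covers both terms in one sentence under Aim 2: "Adherence and compliance will be quantified as the proportion of participants who fully completed the intervention". It defines neither term separately, does not say what full completion consists of, and gives no target or confidence interval. Feasibility results are to be summarised as means with standard deviations or as counts with percentages.

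The intervention is described under Aim 1. Participants receive videos and readings, and each sets up a personal goal-based program. On those goals: "Modifications toward these goals can be made based on progress and discussions with each participant". On delivery: "The contents of the internet-based wellness intervention will be uploaded on Google Classroom". The opening design paragraph describes "multiple assessments across a 10-week intervention period and 1-month follow-up".

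The other Aim 2 tools are:

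- 5-point Likert items, possibly with open-ended questions, at mid-point and end;
- stage of change at the beginning, mid-point and end;
- weekly meetings of investigators and stakeholders on communication with participants, time needed for learning and overall feasibility.

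The same section says that its feasibility components centre on how participants actually use the internet for the intervention. The sample size was set for a different aim: "Our study will recruit 20 participants based on Aim 3".

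**The concern.** Adherence is normally a matter of degree: how much of what was offered was taken up. Retention, meaning who is still in the study, is a separate question. A single completion proportion answers neither cleanly. It discards all information on partial use, and it has no common target when part of the program is individual and adjustable.

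The practical stake is the guidance that the pilot gives to a later trial. A program that half the participants finish and the rest nearly finish calls for a different next step from one that half finish and the rest abandon early. The stated measure returns the same number for both. The opening paragraph presents feasibility information as the study's return if the effects turn out small, so the measure carries some weight.

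**Working it through.** **The plan's own figure.** The only quantitative design statement concerns Aim 3: "which provides 80% power in detecting a large standardized effect size of 0.72", "with an alpha level of 0.05 using a two-sided Wilcoxon Sign-Ranked test", with normal data and 10% drop-out. It reproduces.

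- Analysed n = 20 × (1 − 0.10) = 18.
- Effective n for the signed-rank test under normality = 18 × 3/π = 17.2. Noncentral-t power at d = 0.72 and two-sided alpha 0.05 is 80.1%.
- Simulation of the exact signed-rank test at n = 18 (400,000 replicates) gives 80.2%.

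The sample size is therefore not in question. The documents give no precision figure for the completion proportion.

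**What the measure cannot show.** Let p be the share completing fully and u the average share of content used by the rest. Mean use = p × 100 + (1 − p) × u. The values below are hypothetical, with p = 0.5 (10 of 20).

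- u = 90%: 0.5 × 100 + 0.5 × 90 = 95%.
- u = 10%: 0.5 × 100 + 0.5 × 10 = 55%.

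The reported adherence is 50% in both cases, while mean use differs by 40 points.

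**Whether another tool fills the gap.**

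- Likert items cover satisfaction, intent to continue, interest, recommendation to peers, usability and knowledge. These are opinions, not amount of use.
- Stage of change records readiness.
- Weekly meetings are at team level, and no per-participant usage record is stated.
- The list of potential covariates in the Statistical Analysis section contains no usage variable.

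**Precision of the completion proportion.** The exact (Clopper-Pearson) 95% limits for x of n are the 0.025 quantile of Beta(x, n − x + 1) and the 0.975 quantile of Beta(x + 1, n − x). At n = 20:

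| Completers | 95% CI | Width (points) |
|---|---|---|
| 10/20 | 27.2–72.8% | 46 |
| 16/20 | 56.3–94.3% | 38 |
| 18/20 | 68.3–98.8% | 30 |
| 20/20 | 83.2–100% | 17 |

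**Whether a graded measure would be tighter.** The 95% half-width for a mean is t(0.975, 19) × SD/√20, with t = 2.093. The documents give no SD, so it is worked out here from assumed patterns.

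- Ten participants at 100% and ten at 10%: SD = 45 × √(20/19) = 46.2, half-width 21.6 points. Half the exact interval for 10/20 is 22.8.
- Sixteen at 100% and four at 0%: SD = 40 × √(20/19) = 41.0, half-width 19.2. Half the exact interval for 16/20 is 19.0.
- Ten at 100% and ten at 90%: SD = 5 × √(20/19) = 5.1, half-width 2.4.

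Where non-completers stop early there is almost no gain. A large gain appears only where they nearly finish. The two intervals also estimate different quantities.

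**The case against.** The strongest reply is that this is a declared pilot which makes no precision claim for Aim 2, that demand and implementation are assigned to the Likert items and not to the completion proportion, and that the firm defect is only a missing definition, which one added line would cure.

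Much of this stands. A reader might infer four stronger points that the documents do not support.

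- *That Aim 2 as a whole cannot tell heavy use from none.* The questionnaires, any open-ended items and the weekly meetings may give indirect evidence. The point applies to the adherence and compliance measure.
- *That the yes/no form is what makes the result imprecise.* The half-widths above show that the imprecision comes mainly from n = 20.
- *That a graded measure would explain a positive or null Aim 3 result.* No analysis relating use to outcome is planned, and in a single-arm study of 20 people amount of use would be confounded with motivation.
- *That item-level records are already available.* The plan says only that content is uploaded to the platform, not that completion is marked or can be exported. It also states no weekly unit of completion.

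The reply fails on one matter. A definition alone would not repair the measure, because any cut-off still gives everyone below it the same score. The section sets out to study actual use, yet states no measure of how much use occurred.

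**Conclusion.** The point holds for the stated measure. Applied as written, it gives one ambiguous yes/no figure for two concepts and cannot distinguish near-complete use from none. In the illustration, the same reported 50% is compatible with mean use of 55% or 95%. That range rests on hypothetical values for use among non-completers; the loss of information does not depend on them.

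This is a poor choice of summary as well as an undefined term. It limits what the pilot can report on feasibility. It leaves the Aim 3 sample size and analysis untouched. The change is worth making before launch, because use that is not recorded during the 10 weeks may not be recoverable later. The case rests on information gained, not on better precision.

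**What to change.** Replace the sentence with the following.

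1. **Full completion:** define it against the common content delivered to everyone (videos and readings).
2. **Retention:** the number of the 20 enrolled who attend the end-of-intervention visit and the number who attend the 1-month visit, each with an exact 95% confidence interval.
3. **Adherence:** each participant's percentage of the common content completed over the 10 weeks. Leave individually set goal entries out of the denominator, since including them would bring back a target that varies between people. Count items not done by drop-outs as zero. Show the distribution (median and range, or mean with 95% confidence interval), overall and by week.
4. **Fully-completed proportion:** keep it as a secondary figure, with an exact 95% confidence interval.

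Use the planned pre-launch pilot with 3–5 non-participants to check that the platform can record item completion. If it cannot, use a brief participant completion check.

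The cost is protocol and SAP wording plus either a data export or that check. No extra participants or visits are needed. The main downside is that content used but not marked complete would bias adherence downward, and the report should say so.
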